8.2. Withdrawal from the Study

Participants that are randomized but not dosed with study treatment will be considered for study withdrawal if Day 1 FBF measurement with ACh does not meet quality control criteria or they are unable to complete the initial FBF assessment, including a Day 1 FBF procedure where necessary (See Section 9.6.1.2). These participants will not be considered in the safety analysis as they have not received study treatment. Quality control procedures and criteria are described in the SRM. In all cases, the reason for withdrawal and the date of the last dose will be recorded in the participant's eCRF.

- A participant may withdraw from the study at any time at his/her own request, or may be withdrawn at any time at the discretion of the investigator for safety, behavioral, compliance or administrative reasons.
- If the participant withdraws consent for disclosure of future information, the sponsor may retain and continue to use any data collected before such a withdrawal of consent.
- If a participant withdraws from the study, he/she may request destruction of any samples taken and not tested, and the investigator must document this in the site study records.
- The participant will be asked to attend the follow-up visit 7 to 14 days following the last dose of study treatment. Refer to the SoA (See Section 2) for data to be collected at the time of follow-up and for any further evaluations that need to be completed.

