9.2.1. Time Period and Frequency for Collecting AE and SAE Information

- Any SAEs assessed as related to study procedure (e.g., protocol-mandated procedures, invasive tests, or change in existing therapy) or related to a GSK product will be recorded in the eCRF from the time a participant consents to participate in the study up to and including any follow-up contact.
- AEs and SAEs will be collected from randomization (Day 1) until the follow-up visit at the time points specified in the SoA (See Section [2](#)).
- Medical occurrences that begin before the start of study treatment but after obtaining informed consent will be recorded on the Medical History/Current Medical Conditions section of the eCRF and not the AE section.
- All SAEs will be recorded and reported to the sponsor or designee immediately and under no circumstance should this exceed 24 h, as indicated in [Appendix 4](#). The investigator will submit any updated SAE data to the sponsor within 24 h of it being available.
- Investigators are not obligated to actively seek AEs or SAEs in former study participants. However, if the investigator learns of any SAE, including a death, at any time after a participant has been discharged from the study, and he/she considers the event to be reasonably related to the study treatment or study participation, the investigator must promptly notify the sponsor.
- The method of recording, evaluating, and assessing causality of AEs and SAEs and the procedures for completing and transmitting SAE reports are provided in [Appendix 4](#).

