9.2.3. Follow-up of AEs and SAEs

After the initial AE/SAE report, the investigator is required to proactively follow each participant at subsequent visits/contacts. All SAEs, and non-serious AEs of Special Interest (AESI; as defined in Section 9.2.5), will be followed until the event is resolved, stabilized, otherwise explained, or the participant is lost to follow-up (as defined in Section 8.3). Further information on follow-up procedures is given in Appendix 4.

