10.7.2.1. Handling of Missing and Partial Dates

Element	Reporting Detail
General	
 Partial dates will be displayed as captured in subject listing displays.
Adverse Events	
 The eCRF allows for the possibility of partial dates (i.e., only month and year) to be recorded for AE start and end dates; that is, the day of the month may be missing. In such a case, the following conventions will be applied for calculating the time to onset and the duration of the event: 
 Missing Start Day: First of the month will be used unless this is before the start date of study treatment; in this case the study treatment start date will be used and hence the event is considered On-treatment as per Appendix 4: Study Phases and Treatment Emergent Adverse Events. Missing Stop Day: Last day of the month will be used, unless this is after the stop date of study treatment; in this case the study treatment stop date will be used. Missing Start Month: ‘January’ will be used unless this makes the start date before the month of start of study treatment; in this case the month of study treatment start will be used. Missing Stop Month: ‘December’ will be used, unless this is after the stop date of study treatment; in this case the study treatment stop date will be used.

CONFIDENTIAL

205767

Element	Reporting Detail
	
• Completely missing start or end dates will remain missing, with no imputation applied. Consequently, time to onset and duration of such events will be missing.
Concomitant Medications/Medical History	
• Partial dates for any concomitant medications recorded in the CRF will be imputed using the following convention:
◦ If the partial date is a start date, a '01' will be used for the day and 'Jan' will be used for the month◦ If the partial date is a stop date, a '28/29/30/31' will be used for the day (dependent on the month and year) and 'Dec' will be used for the month.• The recorded partial date will be displayed in listings.

CONFIDENTIAL

205767

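### Minor: the SAP caps a partial AE stop date at the treatment stop date, which can place an AE's end before its onset and cuts short any AE that outlasts treatment

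*SAP*

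**What the plan says.** SAP 10.7.2.1 covers AE dates recorded without a day or month, and states the purpose: "the following conventions will be applied for calculating the time to onset and the duration of the event". For a missing stop day the rule is "Last day of the month will be used, unless this is after the stop date of study treatment; in this case the study treatment stop" (a cap at that date). A missing stop month becomes December, with the same cap. The imputed start date has its own bound: "First of the month will be used unless this is before the start date of study treatment". The imputed stop date has no bound at AE onset, and none appears in SAP Appendix 4 or Appendix 6. Dates that are wholly missing are left missing. In the same section, a partial concomitant-medication stop date goes to the end of the month or year with no treatment cap.

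The protocol expects AEs to begin and end after treatment:
- Section 9.2.1: "AEs and SAEs will be collected from randomization (Day 1) until the follow-up visit".
- Section 9.2.3, for SAEs and non-serious AEs of special interest: they "will be followed until the event is resolved, stabilized, otherwise explained, or the participant is lost to follow-up".
- Section 8.2, for withdrawn participants: "The participant will be asked to attend the follow-up visit 7 to 14 days following the last dose of study treatment".

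SAP 10.4.1 itself defines a post-treatment phase. On display, SAP 10.7.2.1 says: "Partial dates will be displayed as captured in subject listing displays".

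**The concern.** A cap on the end of an AE makes sense only if AEs cannot start or continue after the cap date. Here they can, in both arms. An AE that starts after treatment stops would be assigned an end before it began. One that starts on treatment and persists would appear to resolve on the day treatment stopped. The rule can also override what the site recorded, because an end recorded as a later month is moved back to the month of the treatment stop. What is at stake is the derived AE duration in the analysis dataset. The lack of any similar cap for concomitant medications suggests that the AE cap is not a general convention of this SAP.

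**Working it through.** The plan states no figure to reproduce. The check is date logic, followed by examples.

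**Inputs**
- E = end of the recorded month or year; T = treatment stop date. The rule (SAP 10.7.2.1) is imputed end = the earlier of E and T.
- Assumed for the examples: T = last planned dose, which is Day 28 for darbepoetin and Day 41 for daprodustat (Protocol Section 2, footnote 10).
- Assumed, because the SAP gives no formula: duration = end - onset + 1.
- Follow-up is 7-14 days after the last forearm blood flow procedure (Protocol Section 2, footnote 3): Day 42 + 7 = 49 to Day 42 + 14 = 56, before its own +/- 3 days.

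**1. Complete onset after T, partial end.** E is on or after the true end, which is on or after onset, which is after T. The cap therefore always applies, and the imputed end T is before onset.
- One day after T: darbepoetin Day 29 gives 28 - 29 + 1 = 0; daprodustat Day 42 gives 41 - 42 + 1 = 0.
- Later: darbepoetin Day 35 gives 28 - 35 + 1 = -6; daprodustat Day 45 gives 41 - 45 + 1 = -3.

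**2. Onset on or before T, true end after T, partial end.** E is on or after the true end, so it is after T. The cap always applies and always shortens the event. For a true end on Day 50:

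| Arm | Onset | Imputed duration | True duration |
|---|---|---|---|
| Darbepoetin | Day 20 | 28 - 20 + 1 = 9 | 50 - 20 + 1 = 31 |
| Daprodustat | Day 30 | 41 - 30 + 1 = 12 | 50 - 30 + 1 = 21 |

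**3. Calendar check.** Take Day 1 as 10 January 2019 (assumed). Day 28 is 6 February, Day 35 is 13 February, Day 41 is 19 February, Day 45 is 23 February and Day 50 is 28 February. An end recorded as February imputes to 28 February and is then reset to 6 February (darbepoetin) or 19 February (daprodustat), before the onsets of 13 and 23 February. An end recorded as March is reset to the same February dates, a month earlier than the one recorded.

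**4. Onset days that give a strictly negative duration.** Count the days after T up to follow-up and subtract one for the zero case. These are possible days, not expected errors.
- Darbepoetin completers: 49 - 28 - 1 = 20 to 56 - 28 - 1 = 27.
- Daprodustat completers: 49 - 41 - 1 = 7 to 56 - 41 - 1 = 14.
- Withdrawn participants, either arm: 7 - 1 = 6 to 14 - 1 = 13.

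**5. Enumeration.** Every Day 1 date in 2019 was combined with every complete onset and every true end up to Day 59 (42 + 14 + 3), with the end day missing. End before onset occurred in 100% of post-treatment onsets, and shortening in 100% of AEs that outlasted treatment, in both arms. With the cap removed, no case had its end before onset. If the onset day is also missing, the imputed start is the first of the month (not before treatment start). For post-treatment onsets, the end then precedes that start in about 22% (daprodustat) and 36% (darbepoetin) of cases.

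**The case against.** The main objection is that the cap may never apply. SAP 10.6.2 says that no exposure end date is collected, and SAP 10.4.1 and 10.4.2 treat records with a missing treatment stop date as on-treatment. If the stop date is not populated, there is nothing to cap at and no duration is distorted. This stands as a condition, not as a rebuttal: Protocol 7.6 says that treatment stop dates are recorded in the eCRF, the SAP uses the date in three rules, and its remark on exposure may concern individual dosing records only.

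Materiality is also limited. The SAP was written after termination with 4 completed subjects. AEs are listed only (SAP 7.1), and none of safety Tables 2.1-2.9 is an AE table. Nothing shows that any AE has a partial stop date. All of this stands, and it is why the point is minor.

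Two stronger readings are tempting. First, a reader might infer that reported safety results are wrong. The documents do not support that: partial dates are listed as recorded, and whether any listing prints duration cannot be seen. Second, a reader might infer that the stop date plus 1 day rule makes the treatment-emergent window end earlier for darbepoetin than for daprodustat, and so biases AE reporting between arms. That rests on the stop date being the last dose. The gap would change if dosing is extended for a delayed or repeat procedure (Protocol 9.6.1.4) or a darbepoetin dose is held (Protocol 7.1.1.2), and would vanish if the stop date is missing. No planned display is restricted to treatment-emergent events, since the main AE listing covers all AEs. A new window is therefore not justified here.

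**Conclusion.** The rule is wrong as written, and the point is minor. Given a populated treatment stop date and a partial AE end date, it always places the end before a complete post-treatment onset and always shortens an AE that outlasts treatment, in either arm. These two results need no assumption about which date is the stop date. The day counts and durations shown do: they assume the last planned dose and the end - onset + 1 formula. When the onset day is missing too, the reversal occurs only in some cases; when the end date is wholly missing, nothing is imputed. The consequence is limited to derived AE duration.

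**What to change.** In SAP 10.7.2.1, remove the cap at the treatment stop date from both AE stop rules. Impute a partial AE stop date to the end of the recorded month or year, or to the participant's last recorded study date if that is earlier, and never before AE onset. In the calendar example, if the last recorded study date is not before Day 50, the end becomes Day 50. The two negative durations become 50 - 35 + 1 = 16 days (darbepoetin) and 50 - 45 + 1 = 6 days (daprodustat).

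As a side note, reconcile Protocol 7.6 with SAP 10.6.2 so that the source of the Study Treatment Stop Date is clear.

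The cost is a change of SAP wording and a few lines of derivation code, with no new data and no new tables.

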10.8. Appendix 8: Values of Potential Clinical Importance

10.8.1. Laboratory Values

Hematology				
Laboratory Parameter	Units	Category	Clinical Concern Range	
			Low Flag (< x)	High Flag (>x)
Hemoglobin	g/dL		< 8 g/dL	> 13 g/dL
Platelet Count	GI/L or x10 ⁹ / L		< 80 GI/L	> 500 GI/L
WBC Count	GI/L or x10 ⁹ / L		< LLRR	> 5x ULRR
Neutrophils	GI/L or x10 ⁹ / L		< 0.5 GI/L	
Lymphocytes	GI/L or x10 ⁹ / L		< 0.5x LLRR	

Clinical Chemistry				
Laboratory Parameter	Units	Category	Clinical Concern Range	
			Low Flag (< x)	High Flag (>x)
Albumin	g/L		< 30 g/L	> 55 g/L
AST (SGOT)	U/L			>= 3x ULRR
ALT (SGPT)	U/L			>= 3x ULRR
Total bilirubin	Umol/L			>= 2x ULRR
Potassium	mmol/L		> 0.5 mmol/L below LLRR	> 1.0 mmol/L above ULRR
Sodium (serum)	mmol/L		< 130 mmol/L	> 150 mmol/L

Iron Parameters				
Test Analyte	Units	Category	Clinical Concern Range	
			Low Flag (< x)	High Flag (>x)
Serum ferritin	ug/l		< 100 ug/l	> 800 ug/l
TSAT	Percent		<15%	> 40%

10.8.2. Vital Signs

Vital Sign Parameter (Absolute)	Units	Clinical Concern Range	
		Lower	Upper
Systolic Blood Pressure	mmHg	<= 80 mmHg	>= 160 mmHg
Diastolic Blood Pressure	mmHg	<= 50 mmHg	>= 100 mmHg
Heart Rate	bpm	<= 40 bpm	>= 110 bpm

Note:

At visits where BP and HR are assessed in triplicate, the average of the 3 values will be used to assess PCI criteria.

CONFIDENTIAL

205767

10.8.3. FBF

Agent	Units	Clinical Concern Range			
		FBF Infused Arm		FBF Non-Infused Arm	
		Lower	Upper	Lower	Upper
Saline	mL/min	0.01	15.0	0.01	15.0
ACH	µg/min	0.01	150.0	0.01	30.0
SNP	µg/min	0.01	150.0	0.01	30.0
LNMMA	µmol/min	0.01	15.0	0.01	15.0

10.8.4. PWV

PWV Parameter	Units	Clinical Concern Range	
		Lower	Upper
Average Systolic BP (Seated & Supine)	mmHg	<= 80 mmHg	>= 160 mmHg
Average Diastolic BP (Seated & Supine)	mmHg	<= 50 mmHg	>= 100 mmHg
Central Systolic Pressure	mmHg	<= 80 mmHg	>= 160 mmHg
Central Diastolic Pressure	mmHg	<= 50 mmHg	>= 100 mmHg
Mean Arterial Pressure	mmHg	<= 40 mmHg	>= 200 mmHg
Central Pulse Pressure	mmHg	<= 10 mmHg	>= 200 mmHg
Peripheral Pulse Pressure	mmHg	<= 10 mmHg	>= 200 mmHg
Central Augmentation Pressure	mmHg	<= -50 mmHg	>= 100 mmHg
Central Augmentation Index	%	-30	60
Heart Rate	bpm	<= 40 bpm	>= 110 bpm
Aortic Tr	msec	<=0 msec	>=1000 msec
Carotid to Femoral Distance	mm	<= 200 mm	>= 1500 mm
Pulse Wave Velocity	msec	<= 2 msec	>= 35 msec
Notch to Carotid Distance	mm	<= 10 mm	>= 200 mm
Notch to Femoral Distance	mm	<= 200 mm	>= 1500 mm

CONFIDENTIAL

205767

10.9. Appendix 9: Abbreviations & Trademarks

10.9.1. Abbreviations

Abbreviation	Description
ACH	Acetylcholine,
ADaM	Analysis Data Model
AE	Adverse Event
AIX	Augmentation Index
BP	Blood Pressure
CDISC	Clinical Data Interchange Standards Consortium
CKD	Chronic Kidney Disease
DBF	Database Freeze
DBR	Database Release
DOB	Date of Birth
DP	Decimal Places
eCRF	Electronic Case Record Form
FBF	Forearm Blood Flow
FDA	Food and Drug Administration
FDAAA	Food and Drug Administration Clinical Results Disclosure Requirements
FPD	Future Pipeline Discovery
GSK	GlaxoSmithKline
HR	Heart Rate
ICH	International Conference on Harmonization
IDSL	Integrated Data Standards Library
L-NMMA	L-N ^G -monomethyl arginine citrate
PCI	Potential Clinical Importance
PCPS	Projects, Clinical Platforms, and Sciences
PD	Pharmacodynamic
PDMP	Protocol Deviation Management Plan
PDPP	Pharmacodynamic Per Protocol
PP	Per Protocol
PWV	Pulse Wave Velocity
QC	Quality Control
RAP	Reporting & Analysis Plan
RAMOS	Randomization & Medication Ordering System
rhEPO	Recombinant Human Erythropoietin
SAC	Statistical Analysis Complete
SDTM	Study Data Tabulation Model
SNP	Sodium Nitroprusside
SOP	Standard Operation Procedure
SRM	Study Reference Manual
TFL	Tables, Figures & Listings

10.9.2. Trademarks

Trademarks of the GlaxoSmithKline Group of Companies	Trademarks not owned by the GlaxoSmithKline Group of Companies
NONE	SAS

CONFIDENTIAL

205767

10.10. Appendix 10: List of Data Displays

10.10.1. Data Display Numbering

The following numbering will be applied for RAP generated displays:

Section	Tables
Study Population	1.1 to 1.6
Safety	2.1 to 2.9
Pharmacodynamic	3.1 to 3.10
Section	Listings
ICH Listings	1 to 16
Other Listings	17 to 20

10.10.2. Mock Example Shell Referencing

Non IDSL specifications will be referenced as indicated and if required example mock-up displays provided in [Appendix 11: Example Mock Shells for Data Displays](#).

Section	Table	Listing
Safety	SAFE1	-
Pharmacodynamic	PD_T1 to PD_T5	PD_L1 to PD_L2

NOTES:

- Non-Standard displays are indicated in the 'IDSL / Example Shell' or 'Programming Notes' column as '[Non-Standard] + Reference.'

10.10.3. Deliverables

Delivery	Description
SAC	Final Statistical Analysis Complete

CONFIDENTIAL

205767

10.10.4. Study Population Tables

Study Population Tables					
No.	Population	IDSL / Example Shell	Title	Programming Notes	Deliverable [Priority]
Subject Disposition					
1.1.	Safety	ES1	Summary of Subject Status and Subject Disposition for the Study Conclusion Record	ICH E3, FDAAA, EudraCT	SAC
1.2.	Screened	ES6	Summary of Screening Status and Reasons for Screen Failure	Journal Requirements	SAC
1.3.	Enrolled	NS1	Summary of Number of Participant by Country and Site ID	EudraCT/Clinical Operations	SAC
Demographic and Baseline Characteristics					
1.4.	Safety	DM1	Summary of Demographic Characteristics	ICH E3, FDAAA, EudraCT	SAC
1.5.	Enrolled	DM11	Summary of Age Ranges	EudraCT	SAC
1.6.	Safety	DM6	Summary of Race and Racial Combinations	ICH E3, FDA, FDAAA, EudraCT	SAC

10.10.5. Safety Tables

Safety: Tables					
No.	Population	IDSL / Example Shell	Title	Programming Notes	Deliverable [Priority]
Laboratory: Chemistry					
2.1.	Safety	SAFE1	Summary of Chemistry lab values	ICH E3	SAC
2.2.	Safety	LB1	Summary of Chemistry Changes from Baseline	ICH E3	SAC
Laboratory: Hematology					
2.3.	Safety	SAFE1	Summary of Hematology Values	ICH E3	SAC
2.4.	Safety	LB1	Summary of Hematology Changes from Baseline	ICH E3	SAC

CONFIDENTIAL

205767

Safety: Tables					
No.	Population	IDSL / Example Shell	Title	Programming Notes	Deliverable [Priority]
Laboratory: Other Screening Tests					
2.5.	Safety	SAFE1	Summary of other screen test lab values	ICH E3	SAC
ECG					
2.6.	Safety	SAFE1	Summary of ECG Values	IDSL	SAC
2.7.	Safety	EG2	Summary of Change from Baseline in ECG Values	IDSL	SAC
Vital Signs					
2.8.	Safety	SAFE1	Summary of Vital Signs	ICH E3	SAC
2.9.	Safety	VS1	Summary of Change from Baseline in Vital Signs	ICH E3	SAC

10.10.6. Pharmacodynamic Tables

Pharmacodynamic: Tables					
No.	Population	IDSL / Example Shell	Title	Programming Notes	Deliverable [Priority]
Primary Endpoint					
3.1.	PDPP	PD_T1	Summary of Forearm Blood Flow Ratio in Response to Acetylcholine		SAC
3.2.	PDPP	PD_T2	Summary of Change in Forearm Blood Flow Ratio (Day 1 to Day 42), Acetylcholine		SAC
Principle Secondary Endpoint					
3.3.	PDPP	PD_T3	Summary of Change in Absolute Forearm Blood Flow (Day 1 to Day 42), Acetylcholine		SAC

CONFIDENTIAL

205767

Pharmacodynamic: Tables					
No.	Population	IDSL / Example Shell	Title	Programming Notes	Deliverable [Priority]
Secondary Endpoints					
3.4.	PDPP	PD_T2	Summary of Change in Forearm Blood Flow Ratio (Day 1 to Day 42), Sodium Nitroprusside		SAC
3.5.	PDPP	PD_T3	Summary of Change in Absolute Forearm Blood Flow (Day 1 to Day 42), Sodium Nitroprusside		SAC
3.6.	PDPP	PD_T2	Summary of Change in Forearm Blood Flow Ratio (Day 1 to Day 42), L-NMMA		SAC
3.7.	PDPP	PD_T3	Summary of Change in Absolute Forearm Blood Flow (Day 1 to Day 42), L-NMMA		SAC
3.8.	PDPP	PD_T4	Summary of Augmentation Index and Pulse Wave Velocity		SAC
3.9.	PDPP	PD_T5	Summary of Change in Augmentation Index (Day 1 to Day 42)		SAC
3.10.	PDPP	PD_T5	Summary of Change in Pulse Wave Velocity (Day 1 to Day 42)		SAC

10.10.7. ICH Listings

ICH: Listings					
No.	Population	IDSL / Example Shell	Title	Programming Notes	Deliverable [Priority]
Subject Disposition					
1.	Screened	ES7	Listing of Reasons for Screen Failure	Journal Guidelines	SAC
2.	Enrolled	ES2	Listing of Reasons for Study Withdrawal	ICH E3	SAC
3.	Safety	SD2	Listing of Reasons for Study Treatment Discontinuation	ICH E3	SAC

CONFIDENTIAL

205767

ICH: Listings					
No.	Population	IDSL / Example Shell	Title	Programming Notes	Deliverable [Priority]
Protocol Deviations					
4.	Safety	DV2	Listing of Important Protocol Deviations	ICH E3	SAC
5.	Safety	IE3	Listing of Participants with Inclusion/Exclusion Criteria Deviations	ICH E3	SAC
Demographic Characteristics					
6.	Safety	DM2	Listing of Demographic Characteristics	ICH E3	SAC
Prior and Concomitant Medications					
7.	Safety	CM10	Listing of Concomitant Medications	IDSL	SAC
8.	Safety	MH2	Listing of Medical Conditions	IDSL	SAC
Exposure					
9.	Safety	EX3	Listing of Exposure Data	ICH E3	SAC
Adverse Events					
10.	Safety	AE8	Listing of All Adverse Events	ICH E3	SAC
Serious Adverse Events					
11.	Safety	AE14	Listing of Reasons for Considering as a Serious Adverse Event	ICH E3	SAC
12.	Safety	AE8	Listing of Adverse Events Leading to Withdrawal from Study / Permanent Discontinuation of Study Treatment	ICH E3	SAC
All Laboratory					
13.	Safety	LB5	Listing of All Laboratory Data for Participants with Any Value of Potential Clinical Importance/Outside Normal Range	ICH E3	SAC
14.	Safety	LB14	Listing of Laboratory Data with Character Results	ICH E3	SAC

CONFIDENTIAL

205767

ICH: Listings					
No.	Population	IDSL / Example Shell	Title	Programming Notes	Deliverable [Priority]
ECG					
15.	Safety	EG5	Listing of All ECG Findings for Participants with an Abnormal ECG Finding	IDSL	SAC
Vital Signs					
16.	Safety	VS4	Listing of All Vital Signs Data for Participants with Any Value of Potential Clinical Importance	IDSL	SAC

10.10.8. Non-ICH Listings

Non-ICH: Listings					
No.	Population	IDSL / Example Shell	Title	Programming Notes	Deliverable [Priority]
Primary Endpoint					
17.	PDPP	PD_L1	Listing of Forearm Blood Flow		SAC
18.	PDPP	PD_L2	Listing of All Forearm Blood Flow Data for Participants with Any Value of Potential Clinical Importance		SAC
Secondary Endpoint					
19.	PDPP	PD_L3	Listing of Pulse Wave Velocity and Augmentation Index		SAC
20.	PDPP	PD_L4	Listing of All Pulse Wave Velocity and Augmentation Index Data for Participants with Any Value of Potential Clinical Importance		SAC

CONFIDENTIAL

205767

